5.2 Statistical Analysis Plans

5.2.1 Analysis Sets

5.2.1.1 Safety Population (SP)

The Safety Population (SP), used for all of the safety summaries, is defined as all randomized patients who received at least 1 dose of double-blind study medication. Patients in the SP will be included in the treatment group that they actually received, regardless of their randomized treatment.

5.2.1.2 Modified Intent to Treat (mITT) Analysis Set

The Modified Intent to Treat (mITT) Analysis Set, used for all of the efficacy analyses, is defined as all randomized patients with a baseline lipid value, at least 1 post-baseline lipid value, and having taken 1) their study drug within 2 days prior to the lipid measurement and 2) Repatha 420 mg within 30 days +/- 3 days prior to the lipid measurement. Patients in the mITT analysis set will be included in their randomized treatment group, regardless of the treatment they actually received.

5.2.1.3 Treatment Completer Set

The treatment completer set includes patients who were in mITT analysis set, and received all planned PCSK9i dosing as well as the double-blinded treatment, as indicated on the end of treatment CRF. Sensitivity analysis for primary and secondary efficacy endpoints will be performed using the treatment completer set.

5.2.1.4 Pharmacokinetic Analysis Set (PK)

The PK Analysis Set will include all subjects in the safety analysis set who have at least one PK assessment. These patients will be evaluated for PK concentration summaries unless significant protocol deviations have affected the data or if key dosing or sampling information is missing.

5.2.2 Baseline Definition

Baseline LDL-C, TC, non-HDL-C, [REDACTED] is defined as the average of last two non-missing values within Visit S4 and Day 1 (including unscheduled assessments), if only 1 value is available, then that single value will be used as baseline.

Baseline value for ApoB and hs-CRP will be the Day 1 value.

If missing value presented at Visit S4 or Day 1, then the last non-missing value prior to the first dose of double-blind study medication (including unscheduled assessments) within Visit S4 and Day 1 will be used to compute the baseline for lipid measurements.

Baseline of the laboratory evaluations, vital signs and physical examination is defined as the last non-missing value prior to the first dose of study medication, except baseline of blood pressure is defined as average of measures at same visit.

5.2.3 Protocol Violations and Deviations

A full list of protocol violations and deviations will be compiled and reviewed by the clinical team to identify major versus minor violations/deviations before final database lock. For violations at study entry, patients will be assessed against the inclusion and exclusion criteria of the protocol. For on-study deviations, compliance with the protocol will be examined using blinded review of the database with regard to prohibited therapies, and timing and availability of planned assessments. The determination of major versus minor protocol deviations will be conducted prior to the database lock. Any major protocol deviation will be summarized by treatment group, and all protocol deviation will be listed.

5.2.4 Patient Disposition

Disposition, including reason for withdrawal from the study drug and study, will be summarized by treatment group. In addition, the number of patients who withdraw from the study and withdraw from study drug will be summarized by discontinuation reason.

5.2.5 Demographic and Baseline Characteristics

Demographic information and important patient baseline characteristics including, but not limited to, gender, race, age, baseline vital sign, and baseline lipid parameter values will also be summarized by treatment group.

The following demographic and baseline characteristics will be summarized by treatment group, as well as overall, for safety population and for mITT: age (years), gender, race, ethnicity, height (cm), weight (kg), body mass index (kg/m^2), systolic and diastolic blood pressure (mmHg), heart rate (bpm), fasting lipid parameters (TC [mg/dL], calculated LDL-C [mg/dL], [REDACTED] non-HDL-C [mg/dL] and [REDACTED] ApoB (mg/dL), and hs-CRP (mg/dL). Data will be summarized using descriptive statistics for continuous variables and using counts and percentages for categorical variables by treatment group and overall. Age will be summarized as a continuous variable and by age group (18-40, 41-64, 65-74, and ≥ 75).

5.2.6 Medical History

General medical history will be summarized by treatment group, as well as overall, for safety population and mITT population and presented in a by-patient listing. Where appropriate, terms will be coded using the latest version of Medical Dictionary for Regulatory Activities (MedDRA).

5.2.7 Prior Medications and Concomitant Medications/Procedures

Prior medications are defined as medications that ended prior to the initiation of double-blind study drug. Concomitant medications are defined as medications that were ongoing at the time of double-blind study drug initiation or new medications that started post double-blind study drug initiation and within 30 days following the date of the last dose of study drug.

Medications, including prior statin medications, will be coded using WHO Drug (Sept 2016, or later). The frequency of use of prior medications and use of concomitant medications will be summarized by treatment group, as well as overall, for the safety population according to Anatomical Therapeutic Chemical (ATC) class and preferred term. Prior medications, concomitant medications, and concomitant procedures will be listed for each patient.

5.2.8 Study Drug (ETC-1002 or placebo) Exposure and Compliance

The length of exposure to study drug (ETC-1002 or placebo) will be calculated as the number of days from the first dose of double-blind study drug to the last dose of double-blind study drug, regardless if the patient missed one or more doses of study drug. Length of exposure to study drug during the double-blinded period will be summarized by treatment group using descriptive statistics for the safety population.

The number and percentage of patients who were compliant with taking study drug will be summarized by treatment group and post-baseline time point for the safety population for the following categories <80%; >= 80%. Compliance for study drug will be assessed by counting the number of tablets that are returned as unused study drug and querying the patient regarding daily intake and calculated using the formula: $100 * (\text{Number Dispensed} - \text{Number Returned}) / (\text{Duration in days between study drug dispensed and study drug returned})$. Overall compliance during the study will be calculated by programmer.

Administration and compliance data of the study drug, including reasons for poor compliance, will be listed for each patient.

5.2.9 Repatha Exposure and Compliance

The length of exposure to Repatha for run-in and double-blinded period will be calculated as the number of days from the first dose of Repatha to the last dose of Repatha + 30 days within run-in and double-blinded period, respectively, regardless if the patient missed one or more doses of study drug. The exposure to Repatha (in total doses) will be summarized during the run-in period in an overall group, as well as within the treatment group during the double-blind period. Length of exposure to Repatha (in total doses) for overall group during run-in and by treatment group during double-blinded period will be summarized using descriptive statistics for the safety population.

The number and percentage of patients who were compliant with taking Repatha will be summarized by treatment group for the safety population for the following categories <80%; >= 80%. For Repatha Compliance, it will be calculated using the formula: $100 * (\text{Total number of Repatha administration with } 420 \text{ mg/number of planned injections})$. The number of planned injections are 3 and 2 for run-in and double-blinded period, respectively.

Administration and compliance data of Repatha, including reasons for poor compliance, will be listed for each patient.

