5.4 Safety Endpoints and Analyses

For all safety endpoints, the safety population (SP) will be used. Descriptive summaries will be provided for safety endpoints.

The summarization of AEs will include TEAEs defined as AEs that begin or worsen after the first dose of double-blind study drug administration and ingestion of the first dose of study drug until 30 days after last dose of study drug. The AEs reported during the Repatha run-in period will be summarized separately by overall group. All TEAEs, SAEs, related AEs (to IMP or to Repatha), AEs leading to withdrawal of the study drug or Repatha and study, fatal AEs and AEs of special interest will be summarized by MedDRA System

Organ Class (SOC) and Preferred Term (PT) in descending order of frequency by treatment group.

Clinical safety laboratories, including hematology, blood chemistry, HbA1C, glucose, and urinalysis; PE findings; vital signs; and weight will be summarized by the value and by change from baseline in the value (where appropriate) at each post-baseline time point.

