5.4.1 Adverse Events (AEs)

AEs will be coded using the Medical Dictionary for Regulatory Activities (MedDRA) Version 19.1 or later and will be categorized by MedDRA SOC and preferred term (PT). Patients with AEs that are ongoing at study completion or study withdrawal must be followed until resolution, until stable/chronic, or for 30 days after the last study visit, whichever comes first. Summary tables will focus on TEAEs; however, listings will include all AEs (with non-TEAEs flagged).

In summary tables, TEAEs will be counted as “Not Related” if relationship to IMP was assessed as ‘Not Related’ or “Unlikely”. Events will be counted as “Related” if relationship to IMP was assessed as ‘Possible’, ‘Probable’, ‘Definite’, or if relationship to IMP is missing. TEAEs related to the Repatha will be summarized in the similar fashion.

The severity of the AE will be characterized as mild, moderate, or severe, to the following definitions:

- Mild: Events are usually transient and do not interfere with the patient’s daily activities
- Moderate: Events introduce a low level of inconvenience or concern to the patient and may interfere with daily activities
- Severe: Events interrupt the patient’s usual daily activity, are incapacitating with inability to do usual activities, or significantly affect clinical status and warrant intervention and/or close follow-up

The run-un period will be defined as the period subjects receive Repatha prior to Visit T1. It's 3 months prior to Visit T1.

Overviews of TEAEs will be presented by treatment group containing the following counts and percentages for:

- Patients with AE during the run-in period
- patients with TEAEs
- patients with TEAEs by SOC and PT
- patients with AEs during run-in period by SOC and PT
- patients with TEAEs by maximum severity
- patients with treatment-related TEAEs by IMP or by Repatha
- patients with SAE during the run-in period
- patients with treatment-emergent serious adverse events (TE SAEs)
- patients with TE SAEs by SOC and PT
- patients with SAEs during the run-in period by SOC and PT

- patients with TE SAEs by maximum severity
- patients with treatment-related TE SAEs by IMP or by Repatha
- withdrawal from study drug due to TEAEs
- patients with TEAE by PT
- patients with TE SAEs by PT
- patients with study drug-related TEAEs by PT

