¹ An optional basic fasting lipid MAY be completed prior to S2, but must occur just prior to the next witnessed PCSK9i dose if patient fails to meet lipid entry criterion at Visit S1. If this optional basic fasting lipid is completed, the average of the 2 lipid values will be used to determine eligibility.

² A recheck of blood pressure may be completed prior to T1 if the patient's diastolic blood pressure (DBP) and/or systolic blood pressure (SBP) meet the exclusion criteria levels. Patients may randomize after blood pressure medications have been adjusted, the patients have been on stable doses of blood pressure medications for at least 2 weeks, and the repeat blood pressure values (DBP and/or SBP) do not meet exclusionary values. Repeat labs may be completed prior to T1 to determine eligibility if the patient's estimated glomerular filtration rate (eGFR), alanine aminotransferase (ALT), aspartate aminotransferase (AST) or other labs meet exclusion criteria levels. If this optional lab is completed, the repeated value will be used to determine eligibility.

³ All procedures will be completed for all patients at either EOS if completing the study or early withdrawal.

⁴ Body weight will be measured while fasting, using consistent scales, after voiding, and without shoes and outerwear (eg, coats).

⁶ Vital signs will include DBP, SBP, heart rate (HR) and will be collected prior to any blood sample collection. Patient will rest for 5 minutes prior to assessments

⁷ Serology for HBsAg, HCV-ABV

⁸ Pregnancy test completed in women of child-bearing age only. FSH in naturally postmenopausal women ≥ 1 year without menses and < 55 years;

⁹ Clinical safety labs include hematology, blood chemistry, and urinalysis at all visits. Please refer to laboratory manual for detailed schedule of tests.

¹⁰ Basic fasting lipids include total cholesterol (TC), calculated low-density lipoprotein cholesterol (LDL-C), [REDACTED] non-HDL-C, and [REDACTED].

¹¹ Diet and exercise counseling per local and/or regional guidelines for the management of hyperlipidemia.

¹² Interactive web response system (IWRS) contact at either an early withdrawal or an EOS visit to register study discontinuation visit date.

*Patients must be on PCSK9 for 30 ± 3 days during each month of the PCSK9 run-in period before initiating Day 1.

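### Minor, run-in reporting only: the run-in Repatha exposure table is tied to randomised, dosed patients, and the SAP is inconsistent on whether run-in AE and SAE tables are too

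*SAP*

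**What the plan says.** **Population.** The safety population "is defined as all randomized patients who received at least 1 dose of double-blind study medication" (SAP 5.2.1.1). The other sets in SAP 5.2.1 (mITT, treatment completer, PK) also contain only randomised patients.

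**Run-in exposure.** SAP 5.2.9 calculates length of exposure as the "number of days from the first dose of Repatha to the last dose of Repatha + 30 days", separately for run-in and double-blind periods. It states that this length "for overall group during run-in and by treatment group during double-blinded period will be summarized using descriptive statistics for the safety population". The sentence before it, on total doses, also uses an overall group for the run-in but names no population. Repatha compliance is summarised for the safety population, with 3 planned run-in injections.

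**Entry condition.** Before Day 1, patients must have been on PCSK9 therapy for 30 ± 3 "days during each month of the PCSK9 run-in period before initiating Day 1" (SAP Appendix 1; Protocol 10.2.5 agrees).

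**Run-in AEs.** SAP 5.4 opens with "For all safety endpoints, the safety population (SP) will be used" and then states: "The AEs reported during the Repatha run-in period will be summarized separately by overall group". It also includes "AEs leading to withdrawal of the study drug or Repatha and study" among the events tabulated by treatment group. SAP 5.4.1 continues: "Overviews of TEAEs will be presented by treatment group containing the following counts and percentages for" a list of 16 rows, 4 of which are run-in AE or SAE rows. The paragraph after the list bases overview percentages on the safety population. The AE listings cover all AEs and name no population. SAP Section 6 records the run-in AE summary as an addition to the protocol.

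**The concern.** The run-in is when every participant starts Repatha, and the design foresees that some will not be randomised. SAP 4.1 screen-fails patients with LDL-C below 70 mg/dL at S4, and Protocol 6.6.1 anticipates AE follow-up of patients who fail after starting the run-in. Reaching randomisation can also depend on safety findings: Protocol 7.2 excludes patients with unexplained CK elevation up to randomisation (criterion 12), or with a medical finding that the investigator thinks may compromise safety (criterion 20).

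A table labelled as the overall run-in group will be read as describing everyone given Repatha. If it holds only patients who got through the run-in and were then dosed, it leaves out those who left early, including any who left because of an adverse event. At stake is the accuracy of the run-in description that the sponsor chose to add.

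**Working it through.** The documents give no figure for this point, so there is none to reproduce. The check sets the provisions side by side and works out what the exposure table can contain.

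**1. Run-in exposure by the SAP's own rule.** Inputs: injections at S2, S3 and S4 (Protocol 9.2); intervals of 30 ± 3 days, so 27 to 33 (Protocol 10.2.2); length = last run-in dose − first run-in dose + 30 days (SAP 5.2.9).

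| Run-in doses | Length of exposure (days) | Run-in compliance |
|---|---|---|
| 1 | 0 + 30 = 30 | 100 × 1/3 = 33% |
| 2 | (27 to 33) + 30 = 57 to 63 | 100 × 2/3 = 67% |
| 3 | 2 × (27 to 33) + 30 = 84 to 96 | 100 × 3/3 = 100% |

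The entry condition puts safety-population patients in the last row, apart from protocol deviations. Patients who stopped for good after one or two doses cannot appear.

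**2. Who is omitted.** Patients who withdraw during the run-in, fail at S4, or fail at T1. S4 failures would normally have had three doses: the injection is given at the end of that visit (Protocol 10.2.4), while the deciding LDL-C must come from the central laboratory, whose S1 results are described as taking several days (Protocol 10.2.1).

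**3. Run-in AEs and SAEs.**

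| Provision | Points to |
|---|---|
| 5.4: safety population for all safety endpoints | randomised and dosed only |
| 5.4: run-in AEs separately, overall group | no population named; could mean all Repatha recipients |
| 5.4.1: 4 of 16 overview rows under a by-treatment-group heading | randomised only, as others have no treatment group |
| 5.4.1: percentages on the safety population | randomised and dosed only |

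Three of the four point to the safety population, and the remaining one does not fit the heading in 5.4.1. SAP 5.4.1 also defines the run-in relative to Visit T1, so the period has no stated end for patients without a T1.

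**4. Effect on a run-in AE percentage.** Let f be the share of Repatha recipients outside the safety population, p_R the AE risk in patients inside it and p_U the risk in those outside. The percentage among all recipients is (1 − f)p_R + f·p_U, and the safety-population percentage is p_R. The difference is f × (p_U − p_R): zero if the risks are equal, and of either sign otherwise. The documents give none of these values.

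For scale only, assume f and that all 52 planned patients are randomised and dosed. Recipients = 52/(1 − f), rounded up:

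| Assumed f | Repatha recipients | Outside the tables |
|---|---|---|
| 10% | 58 | 6 |
| 30% | 75 | 23 |
| 50% | 104 | 52 |
| 70% | 174 | 122 |

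**The case against.** Only the length-of-exposure sentence in 5.2.9 expressly names the safety population for a run-in overall group. The sentence before it names none. For AEs, SAP 5.4 sets the run-in apart as a separate overall-group summary, and the by-treatment heading in 5.4.1 introduces overviews of TEAEs, which run-in events are not. A reader might infer that the SAP definitely excludes unrandomised patients from the run-in AE tables. The text does not settle that, so the AE half stands as an inconsistency with a most natural reading.

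Other strong inferences also fail:

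- **That these patients' events are lost.** The listings are not restricted to the safety population, and Protocol 12.2.2 requires SAE reporting from consent until 30 days after completion or discontinuation.
- **That a planned run-in withdrawal table must show zero.** None of the four run-in rows concerns withdrawal.
- **That screen failures have no scheduled AE assessment after their last dose.** AEs are assessed at T1 before the final eligibility review, and at S3 and S4 before the injection. Patients who fail at T1, or stop at S3 or S4 before being injected, are therefore assessed.
- **That the exposure table has no variation at all.** SAP 5.2.9 allows for missed doses and poor compliance, and Protocol 10.3.2 for early or late visits.

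The materiality argument is also fair: the safety objective compares bempedoic acid with placebo, and the protocol itself plans no run-in AE table. That sets the rating. It does not remove the mismatch between the table's label and its population.

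**Conclusion.** The point holds as a minor one, confined to run-in reporting. For length of Repatha exposure the restriction is explicit, and the resulting table describes patients selected for completing the run-in: essentially 3 doses and 84 to 96 days, apart from deviations. For run-in AEs and SAEs the SAP is inconsistent. On the most natural reading, unrandomised recipients are missing from numerators and denominators, including any who left because of a run-in AE.

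The exposure range rests on the 30 ± 3 day interval and the SAP's 30-day addition. The recipient counts above rest on assumed attrition and are not estimates for this trial. Neither size nor direction of bias in a run-in AE percentage can be stated. No objective asks for a run-in rate, and the primary analysis and the randomised safety comparison are untouched.

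**What to change.** 1. **SAP 5.2.1:** add a Run-in Safety Set, defined as all patients given at least one study-provided Repatha dose, randomised or not.
2. **SAP 5.2.9, 5.4 and 5.4.1:** use this set as numerator and denominator for run-in Repatha exposure, run-in compliance, AEs and SAEs. Show one overall group, and also split by randomised or not. Keep the safety population for TEAEs and double-blind compliance.
3. **SAP 5.4.1:** move the four run-in rows out of the by-treatment-group overviews, and limit the safety-population denominator to treatment-emergent rows.
4. **SAP 5.4.1:** state where the run-in ends, for analysis, in patients never randomised. One option is the last run-in Repatha dose + 30 days, in line with 5.2.9, or last contact if earlier.
5. **Table footnote:** AE follow-up after the last run-in dose may be shorter or less complete in unrandomised patients, because screen failures need not attend further visits.

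The cost is SAP wording, one set flag and a few extra tables, with no new procedures. The limitation is data completeness. AEs are to be collected from consent, with relationship to PCSK9i (Protocol 12.1.3). But screen failures need not return (Protocol 10.2.5), or only may be asked to (6.6.1), and Protocol 17.3 expressly requires a completed eCRF only for patients who receive study drug, a term the Synopsis uses for bempedoic acid or placebo. Check before database lock that AE and injection records for run-in-only patients are in the database.

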5.3 Efficacy Endpoints and Analyses

5.3.1 For all efficacy endpoints and analyses, the Modified Intent to Treat (mITT) analysis set will be used. Primary Endpoint Analysis

The primary efficacy endpoint is the percent change from baseline to Month 2 in LDL-C. If triglycerides (TG) > 400 mg/dL or LDL-C < 50 mg/dL, LDL-M instead of LDL-C will be used as primary efficacy endpoint. The primary efficacy endpoint will be analyzed using analysis of covariance (ANCOVA), with treatment group as a factor and baseline LDL-C as a covariate. The ANCOVA will be performed using the mITT, with patients included in their randomized treatment group regardless of the treatment they actually received. Patients who are missing their Month 2 LDL-C will have their Month 2 value imputed by last post-baseline observation carried forward (LOCF). The least squares mean (LSM) and standard error (SE) for percent change estimate will be provided for both treatment groups, along with the placebo-corrected LSM, its 95% confidence interval (CI) and associated p-value.

The ANCOVA assumptions will be examined and nonparametric test or transformation of the data will be considered if these assumptions are not met. A non-parametric approach using Wilcoxon rank sum test will be performed on percent change from baseline for hs-CRP and TG. The median treatment difference (location shift) and 95% CI from Hodges-Lehmann estimates will be also presented.

An example sas code for ANCOVA analysis is shown as below:

```
PROC MIXED DATA=adxx method=reml;  
  class usubjid armcd;  
  model pchg = blres armcd / solution ddfm=kenwardroger;  
  repeated/group=armcd;  
  lsmeans armcd / diff cl;
```

Missing data for the primary endpoint will be imputed using the last post-baseline observation carried forward (LOCF) procedure (only post-baseline values will be carried forward).

A secondary analysis for the primary endpoint will be conducted use observed data only.

The same analysis will be performed as sensitivity analysis on treatment completer set for primary efficacy endpoint.

The mean (\pm SE) will be plotted for primary efficacy endpoint by visit.

